**Title: Intervention With Vitamin D and Omega-3 Supplements and Incident Heart Failure**

**NCT #: NCT02271230**

**Date: December 31, 2020**

# Study Protocol and Statistical Analysis Plan

## 1. Overview of parent VITAL

VITAL is an ongoing and NIH-funded (R01 CA138962) randomized, double-blind, placebo-controlled trial using a 2x2 factorial design to test the effects of 2,000 IU/d of vitamin D and 1 g/d of EPA/DHA (EPA: DHA ratio of 1.3:1) supplements in the primary prevention of cardiovascular disease and cancer among 25,871 men and women during 5 years of treatment and follow-up.

**Enrollment, eligibility, run-in, and randomization.** For enrollment into VITAL, 1.2 million ethnically and racially diverse people, including health professionals, AARP members, *Essence* subscribers, professionals, college-educated individuals, and Black business professionals, were mailed a detailed description of VITAL's objectives, an informed consent form, a brief questionnaire, and a self-addressed, pre-paid envelope for returning the forms. Eligibility criteria for VITAL included (1) age  $\geq 50$  (men) or  $\geq 55$  (women); (2) no history of cancer (except non-melanoma skin cancer), myocardial infarction, stroke, transient ischemic attack, angina pectoris, coronary artery bypass graft, or percutaneous coronary intervention; (3) no history of safety exclusions: kidney stones, renal failure or dialysis, hypercalcemia, hypo- or hyperparathyroidism, severe liver disease, sarcoidosis, active chronic tuberculosis, or Wegener's granulomatosis; (4) no allergy to fish (for EPA+DHA); (5) no other serious illness that would preclude participation; (6) consumption of  $< 800$  IU vitamin D from all supplemental sources combined; (7) current intake of  $< 1.2$  g/d of calcium from all supplemental sources combined; (8) not taking fish oil supplements; and (9) ability to sign the informed consent form. **Table 1** shows baseline characteristics of VITAL participants.

A **run-in** phase was designed to eliminate poor compliers prior to randomization to increase statistical power. Willing and eligible participants were mailed placebo for vitamin D and EPA/DHA to assess potential compliance and side effects. After 3 months, a follow-up questionnaire was used to query about continued eligibility, willingness, compliance, and potential side effects. Non-responders were mailed 2nd and 3rd requests.

For **randomization** into VITAL, participants are required to be: (i) compliant (taking two-thirds or more of the study pills during run-in); (ii) willing to continue; (iii) eligible based upon the above criteria; and (iv) willing to limit supplemental vitamin D intake and forego fish oil supplements. Randomization is being stratified by 5-year age groups, and in blocks of 8 individuals, with 2 individuals in each of the 4 treatment combinations. Pilot mailings indicated that 40,000 individuals, including  $> 10,000$  minority participants, were willing and eligible for the run-in, of whom 65% ( $n = \sim 26,000$ ) were compliant and remained willing and eligible for randomization.

**Baseline questionnaire and food frequency questionnaire (FFQ):** Each VITAL participant completed a comprehensive baseline questionnaire to collect information on demographics, medical history, medication use, vitamin D, fish oil, and other supplement use, lifestyle and clinical risk factors, and potential effect modifiers of vitamin D such as skin pigmentation and sunlight exposure. A self-administered FFQ was also mailed to participants during the run-in. The FFQ has been shown to be an efficient and valid instrument to assess individuals' diet and to derive nutrients. To capture changes in dietary habits over time, a second FFQ will be administered to all VITAL participants at 24 months of follow up. Average dietary intake of vitamin D, EPA, and DHA and other important nutrients will be estimated from the FFQ for proposed analyses.

**Baseline and follow-up blood collection:** Blood collection kits were sent to willing subjects during the run-in period to collect fasting blood samples; subjects were asked to record the time of venipuncture and their last meal. Collected blood samples are being sent back to our laboratory in freezer packs within 24 hours of blood collection. Upon receipt, we process and aliquot these specimens into multiple vials that are then kept at  $-170^{\circ}$  Celsius in liquid nitrogen. Blood samples are processed within hours of receipt to ensure that samples are frozen within 30-36 hours after venipuncture. In addition, a random sample of 2,000 individuals will have follow-up blood drawn after 24 and 48 months of follow-up at the Boston Clinical and Translational Science Center

**Table 1.** Baseline characteristics of VITAL cohort ( $n=25,874$ )

Male	50%
Mean age ( $\pm$ SD) -Years	67 $\pm$ 7
Mean BMI ( $\pm$ ) - kg/m 	29 $\pm$ 6
Non-Hispanic White	71%
African Americans	20%
Age $\geq 65$	63%
$\geq$ High school graduate	99%
Exercise (MET/week)	15
Any alcohol use	69%
Aspirin use	45%
Income $< \$15,000$	6%
Use of multivitamin	44%
Current smoker	4%
History of diabetes	13%
Prevalent hypertension	53%
Current statin use	37%

(CTSC) to assess compliance and changing trends in background fortification with vitamin D and marine omega-3 fatty acids, as well as to evaluate physiologic changes in selected biomarkers. To date, we have collected baseline blood collection 16,361 VITAL participants.

Quality assurance and follow up. Quality assurance testing ensures that the intervention (vitamin D and EPA/DHA) contains the correct doses and is free of contaminants. At 6 months and at each anniversary date of randomization, each participant will receive a follow-up questionnaire and a re-supply of study treatments. Each annual follow-up questionnaire assesses compliance, use of non-trial vitamin D and fish oil, dietary intake of vitamin D and fish, information on interim medication use, physical activity, weight, comorbidity including HF, etc. Data on potential side effects are being collected and tracked by a Data and Safety Monitoring Board. Non-respondents receive multiple mailed requests, followed by a telephone call to collect data. For non-respondents, vital status will be ascertained. To further test compliance, 250 VITAL subjects residing in New England will receive unannounced visits to draw bloods to measure plasma vitamin D and EPA/DHA.

## **2. Follow-up and adjudication procedures for HF (requiring hospitalization) and recurrent HF hospitalizations.**

The main method of follow-up is mailed questionnaires and review of medical records to confirm study endpoints. Participants receive follow-up questionnaires at 6 months and 1 year after randomization and annually thereafter. A new supply of study pills is mailed with each annual questionnaire. The questionnaires ask about compliance with randomized treatments, use of non-study supplements of vitamin D and marine omega-3 fatty acids, development of major illnesses including HF, cancer and CVD, and potential side effects of the study agents. Non-responders receive two additional requests by mail and are then telephoned to collect study data. At a minimum, vital status is ascertained.

Participants who report a HF diagnosis are asked to sign a medical release for relevant medical records. An Endpoints Committee of physicians blinded to treatment assignment (including Drs. [name], [name], and [name]) will review the records to confirm or disconfirm the diagnosis of HF. Deaths are confirmed by convincing evidence from available sources, including death certificates, hospital records, autopsy reports, and for deaths outside the hospital, observer accounts. For deaths reported by family members, the next-of-kin is asked to provide medical records and a copy of the death certificate. If the latter is not provided, a copy is obtained from the appropriate state vital records bureau. If records are not available (or if participants are lost to follow-up), we search the National Death Index Plus to obtain an International Classification of Disease-coded cause of death based on death-certificate information.

We will **use criteria outlined by the American College of Cardiology/American Heart Association Task Force on Clinical Data Standards** to define HF. This definition requires **ALL** of the following **four elements** to be met:

1. Patient's admission to the hospital with a primary diagnosis of HF
2. New or worsening symptoms due to HF on presentation including at least **ONE** of the following: dyspnea, worsening peripheral edema, decreased exercise tolerance, fatigue, and other symptoms of worsened end-organ perfusion or volume overload
3. At least **TWO physical signs** (including rapid weight gain, pulmonary rales, increased jugular venous pressures and/or hepatjugular reflux, peripheral edema, increasing abdominal distension or ascites in the absence of primary liver disease, and S3 gallop) or **ONE physical sign plus at least ONE laboratory criterion** obtained within 24 hours of presentation (increased B-natriuretic peptide, radiologic evidence of pulmonary congestion, and non-invasive or invasive diagnostic evidence of elevated left- or right-sided ventricular filling pressure or low cardiac output)
4. Patient receives initiation or intensification of HF treatment including at least **ONE** of the following [(i) significant augmentation in oral diuretic therapy, (ii) intravenous diuretic, inotrope, or vasodilator therapy, and (iii) mechanical or surgical intervention such as mechanical circulatory support or mechanical fluid removal].

The same definition will be used to adjudicate recurrent HF hospitalizations. Once pertinent information has been abstracted from the medical records using the data form, two physician adjudicators will review each chart independently, followed by a joint meeting of the entire HF Endpoint Committee to discuss cases where disagreement exists among the two reviewers. Here, we will adopt a simple majority vote. Each event will be

evaluated for presence of HFpEF (EF $\geq$  50%) or HFrEF (EF<50%) based on ejection fraction (EF) obtained during the index hospitalization. Whenever possible, we will assign the etiology of HF (i.e., valvular, arrhythmia, coronary artery disease, etc).

### Linkage to the Centers for Medicare & Medicaid Services (CMS)

To supplement the number of self-reported HF from follow-up questionnaires, we will also identify VITAL participants (mean age 67 y) with incident HF by linking our data with the CMS database. We will use HF diagnoses (ICD-9 codes 428) for such linkage. Costs associated with CMS linkage are covered by the parent VITAL trial. Each year, we will obtain Medicare Data Files through ResDAC, a CMS contractor for academic researchers. Although CMS might be more likely to capture older subjects (65+ years), women, and white participants, we anticipate equal proportion of subjects randomized to either intervention or corresponding placebo given randomization and a large sample size. Hence, the difference between intervention and placebo should remain constant.

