### Statistical analyses by specific Aim

#### **Primary Aim 1** Quantify the effects of vitamin D3 intervention vs. placebo on incidence rate of HF.

**Hypothesis:** *Intervention with vitamin D3 reduces the incidence rate of HF among VITAL participants.*

**Study design:** Randomized double-blind, placebo-controlled, 2x2 factorial trial of vitamin D3 and EPA/DHA.

**Study subjects:** Participants included in the VITAL (n=25,871).

**Primary outcome:** Incidence of HF hospitalization

**Statistical model:** We will exclude any prevalent HF at baseline and use Cox proportional hazards model to estimate effects. Time-to-event will be calculated as the interval between time of randomization and the earliest of: 1) HF incidence, 2) death, or 3) end of the study. Analyses of treatment effects will be based on the intent-to-treat principle. The first analysis will compare baseline characteristics by randomized treatment assignment to ensure that balance was achieved by the randomization. Characteristics to be examined include known risk factors for HF, such as age; gender; race/ethnicity; body mass index; smoking; alcohol use; physical activity; medical conditions such as hypertension, hyperlipidemia, diabetes, and family history of coronary disease; and baseline vitamin D and omega-3 fatty acid levels as assessed by FFQ. The large sample size, as well as successful balance of known potential confounders, will provide assurance that unmeasured or unknown potential confounders will also be equally distributed across randomized treatment groups

In this 2x2 factorial design, the primary aim is to compare the main effects of intent-to-treat with vitamin D3 on incidence rate of HF. We will use the Cox proportional hazards model to allow for variable follow-up lengths and will estimate the hazard ratio for vitamin D3 intervention using indicators for treatment exposure, controlling for EPA/DHA intervention, age, and gender. Because the cohort will consist of older individuals,

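### Could Medicare-only ICD-9 428 cases enter the primary endpoint unconfirmed and dilute the hazard ratio?

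*Combined protocol and SAP*

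**What the plan says.** The primary outcome under Primary Aim 1 is "Incidence of HF hospitalization", analysed by a Cox model; Primary Aim 2 uses the same model. Section 2 defines an HF event by four elements, all required. The first is "admission to the hospital with a primary diagnosis of HF"; the others are symptoms, physical signs with or without laboratory evidence, and treatment started or intensified. The same section names mailed questionnaires and "review of medical records to confirm study endpoints" as the main method of follow-up. Two physicians review each chart independently, and the full blinded committee settles disagreements. Each event is also classed as preserved or reduced ejection fraction, "based on ejection fraction (EF) obtained during the index hospitalization".

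On obtaining records, Section 2 says: "Participants who report a HF diagnosis are asked to sign a medical release for relevant medical records".

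The subsection on linkage to the Centers for Medicare & Medicaid Services (CMS) gives its purpose as "To supplement the number of self-reported HF from follow-up questionnaires" and its method as "We will use HF diagnoses (ICD-9 codes 428) for such linkage". It names no care setting, code position or confirmation step. It accepts that Medicare may capture older, female and white participants more fully, expects equal proportions by arm, and concludes: "Hence, the difference between intervention and placebo should remain constant".

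**The concern.** A diagnosis code cannot show symptoms, signs or treatment. Without a limit to inpatient or principal diagnoses, it cannot show the first element either. A case found only in claims was not self-reported, so the one stated trigger for a medical release does not reach it, and no sentence says what becomes of it. On one reading, the code alone makes the participant a primary event.

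The reassurance in the CMS subsection does not exclude harm on that reading. Balance by arm protects different scales against different errors. Equal under-capture leaves the HR essentially unchanged but shrinks the rate difference. Equal numbers of false positives leave the rate difference unchanged but move the HR toward 1. Because both primary aims are estimated by the HR, unconfirmed codes could attenuate the main result, and the choice of event set could be left until results are known.

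**Working it through.** **Inputs from the plan (Primary Aim 1, statistical power, and Table 2).** 25,871 participants, equal allocation (12,935.5 per arm for each main effect), mean follow-up 5 years, 8.29 cases per 1,000 person-years, two-sided 5% log-rank test, observed relative risk 0.82, stated power 80%.

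**Reproducing the plan's figure.** Power = Φ(½·√D·|ln HR| − 1.96), with D the total number of events.

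- Stated inputs as they stand: control events = 12,935.5 × 5 × 0.00829 = 536.2; D = 536.2 × 1.82 = 976; power 87.3%, not 80%. Exponential event times give 957 events and 86.7%.
- Events multiplied by a further 0.8: control events 428.9; D = 780.7; power 79.2%. This factor reproduces all 22 power entries in Table 2 to within one point, but the documents do not state it. I use it only to stay on the table's scale.

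**Effect of each error type by scale (8.29 per 1,000, HR 0.82).** The true rate difference is 8.29 × (0.82 − 1) = −1.49 per 1,000 person-years.

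- Capture of 80% in both arms: HR 0.82; rate difference 0.8 × (−1.49) = −1.19.
- False positives at 2.07 per 1,000 in both arms (20% of counted control-arm events): rate difference still −1.49; HR = (8.29 × 0.82 + 2.07)/(8.29 + 2.07) = 0.856.

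**Effect of counting claims cases.** Assumptions not in the documents: claims add a fraction A = 0.25 to control-arm events, on top of the planned rate; a share q of them meets the definition, with HR 0.82; the rest have HR h.

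- Count every code: HR = [0.82(1 + Aq) + hA(1 − q)]/(1 + A); D = 428.9(1 + A)(1 + HR).
- Count confirmed cases only, all qualifying records retrieved: HR 0.82; D = 780.7(1 + Aq).

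| q | Count all, h = 1: HR | Power | Count all, h = 0.90: HR | Power | Confirmed only: power (HR 0.820) |
|---|---|---|---|---|---|
| 0 | 0.856 | 68.9% | 0.836 | 80.2% | 79.2% |
| 25% | 0.847 | 74.3% | 0.832 | 82.2% | 81.5% |
| 50% | 0.838 | 79.2% | 0.828 | 84.0% | 83.7% |
| 75% | 0.829 | 83.6% | 0.824 | 85.7% | 85.6% |
| 100% | 0.820 | 87.3% | 0.820 | 87.3% | 87.3% |

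Example, q = 0 and h = 1: HR = (0.82 + 0.25)/1.25 = 0.856; D = 428.9 × 1.25 × 1.856 = 995; power 68.9%.

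**Sensitivity.**

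- With h = 1, counting every code costs power against no linkage only if fewer than about half of the added cases qualify (break-even q 51%, 50% and 48% when claims add 11%, 25% and 43%).
- With h = 0.90, power is above 79.2% at every q. With h = 0.82 the HR does not move.
- Without the 0.8 factor the HRs are identical. The h = 1 powers at q = 0, 25% and 50% become 78.3%, 83.2% and 87.3%, against a base of 87.3%.
- Confirmed-only counting is not free. At q = 75% and h = 1 it has less power than counting every code if fewer than about 65% of qualifying records are retrieved.

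**Which reading does the text support?** The four-element definition admits no exception by source. Claims supplement self-reports, and Section 2 has the committee confirm or reject self-reports from records. Classification by ejection fraction needs a chart for every event. All three point to claims as a way of finding cases that then go to adjudication.

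**The case for a change.** The strongest argument for acting is that adjudication of claims cases is inferred, not written. Section 2 ties the medical release to self-report. For deaths it does state a fallback when records are missing (coded cause from the National Death Index Plus), so silence on the equivalent question for claims is noticeable. One sentence would close the gap, and without it the event set for two primary aims could in principle be settled after results are known.

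The omission stands, and so does the point about scale: equal capture by arm would not protect the HR from false-positive codes. Three things limit what follows.

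- Counting bare codes would contradict the plan's own definition. It is not an equally open option.
- Attenuation needs both a true effect and non-qualifying cases that do not respond to treatment. Under the null there is no bias. A case can fail the definition because HF was managed outside hospital or was not the primary diagnosis, and such a case may respond.
- The sentence about a constant difference answers unequal capture by age, sex and race. For that problem the HR is indeed essentially unaffected, and rewording the sentence would alter no result.

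Limiting the search to inpatient claims with the code in the principal position would go beyond the gap. Once cases are adjudicated, such a filter is not needed to remove false positives, and it would discard true admissions coded in a secondary position.

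**Conclusion.** No change is called for. This is a missing procedural detail that analysts following the stated endpoint would fill sensibly: claims cases go through record review and count only if they meet all four elements. On that reading the HR stays at 0.82 and linkage adds power, from 79.2% up to 87.3% under the 25% assumption if every added case qualifies and its record is retrieved.

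On the less likely reading, with codes counted unconfirmed, the HR would move from 0.82 to at most 0.856 when claims add 25%. If half to three quarters of the added cases qualify, it would be 0.838 to 0.829, with power unchanged or higher (79.2% to 83.6%). These sizes rest on the added fraction, the qualifying share and an HR of exactly 1 for non-qualifying cases, none of which the documents give; the absolute powers also rest on the unstated 0.8 factor. The documents therefore show neither that bare codes would be counted nor how large any dilution would be.

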## **3. Research Design and Methods**

### Measurement of other important variables

Information on demographics, anthropometrics, lifestyle factors, family history of coronary artery disease, and comorbidity will be obtained at baseline and during follow-up via study questionnaires.

### Data management and cleaning

Our team has developed a sophisticated computer system to create and maintain data. A computing system tracks each participant's stage and level of participation in VITAL by automatically generating letters, questionnaires, and phone call reminders. Questionnaires are being optically scanned using TELEform and Alchemy (Cardiff Software) programs, which have been successfully used for our other mail-based clinical trials (PHS, WHS). Out-of-range, internally inconsistent, and unclear data are reviewed and corrected as necessary. Unscannable forms and name or address changes are double entered into the system. All data undergo additional within-form and across-time checks to verify accuracy. The VITAL database will be maintained on a UNIX server that is backed up nightly, ensuring at least two current copies at all times.

Data entry is performed using formatted screens with built-in error checking. Each follow-up questionnaire is entered by two different persons. The two generated files are compared using an interactive verification program that allows for immediate correction of any discrepancies. Before being added to the database, the data undergo further within-form and across-time verifications to assure completeness, accuracy, and participant identification number. Any errors in coding or keying are corrected promptly.

### Statistical analyses by specific Aim

#### **Primary Aim 1** Quantify the effects of vitamin D3 intervention vs. placebo on incidence rate of HF.

**Hypothesis:** *Intervention with vitamin D3 reduces the incidence rate of HF among VITAL participants.*

**Study design:** Randomized double-blind, placebo-controlled, 2x2 factorial trial of vitamin D3 and EPA/DHA.

**Study subjects:** Participants included in the VITAL (n=25,871).

**Primary outcome:** Incidence of HF hospitalization

**Statistical model:** We will exclude any prevalent HF at baseline and use Cox proportional hazards model to estimate effects. Time-to-event will be calculated as the interval between time of randomization and the earliest of: 1) HF incidence, 2) death, or 3) end of the study. Analyses of treatment effects will be based on the intent-to-treat principle. The first analysis will compare baseline characteristics by randomized treatment assignment to ensure that balance was achieved by the randomization. Characteristics to be examined include known risk factors for HF, such as age; gender; race/ethnicity; body mass index; smoking; alcohol use; physical activity; medical conditions such as hypertension, hyperlipidemia, diabetes, and family history of coronary disease; and baseline vitamin D and omega-3 fatty acid levels as assessed by FFQ. The large sample size, as well as successful balance of known potential confounders, will provide assurance that unmeasured or unknown potential confounders will also be equally distributed across randomized treatment groups

In this 2x2 factorial design, the primary aim is to compare the main effects of intent-to-treat with vitamin D3 on incidence rate of HF. We will use the Cox proportional hazards model to allow for variable follow-up lengths and will estimate the hazard ratio for vitamin D3 intervention using indicators for treatment exposure, controlling for EPA/DHA intervention, age, and gender. Because the cohort will consist of older individuals,

competing risks due to deaths from other causes will be considered. The primary analysis will estimate the cause-specific hazard and the hazard ratio comparing intervention groups for HF by censoring individuals with deaths due to competing causes. To estimate the cumulative incidence function, the subdistribution of HF will be plotted over time. The alternative Fine and Gray approach models the effect of treatment on the subdistribution hazard or directly on the cumulative incidence function. While we will consider this and compare its fit to the model-free cumulative incidence curves, the proportional hazards approach will be our primary analysis. Beyond the primary analyses, we will examine effect modification by EPA/DHA intervention, baseline risk factors, and time.

**Statistical power:** We computed statistical power assuming a) 2x2 factorial trial of 25,871 subjects at risk; b) equal and independent treatment allocation; c) mean follow-up of 5 years with minimal loss to follow-up; d) incidence rate of 8.29 cases per 1,000 person-years (40% of the rate reported in the ARIC and CHS studies (21/1000 person-years) in order to account for healthy volunteer effect in VITAL) , and e) a non-compliance rate of 20%. We also used 30% [6.19 cases /1,000 person-years] of the rates seen in the ARIC and CHS to be more conservative. We used a log-rank analysis with a 2-tailed p-value of 0.05. We have 80% power to detect a 18% reduction in the incidence of HF (**Table 2**).

Observed RR*	0.82	0.81	0.80	0.79	0.78	0.77	0.76	0.75	0.74	0.73	0.70
True RR†	0.78	0.76	0.75	0.74	0.73	0.71	0.70	0.69	0.68	0.66	0.63
Power (rate 8.29/1000)	80	84	87	91	93	95	96	98	98	99	>99
Power (rate 6.19/1000)	67	72	76	81	84	87	90	92	94	96	99

\*Observed RR=intent-to-treat relative risk with 80% compliance; †True RR=Relative risk under perfect compliance

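### Does the time-to-event rule need a separate censoring date for living participants whose heart failure status is no longer known?

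*Combined protocol and SAP*

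**What the plan says.** Section 3, Primary Aim 1, Statistical model, runs time from randomization to "the earliest of: 1) HF incidence, 2) death, or 3) end of the study". The only other censoring that section names is at death from a competing cause. It also says why the model was chosen: the "Cox proportional hazards model to allow for variable follow-up lengths". Primary Aim 2 reuses this model.

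On participants who stop replying, Section 2 says: "Non-responders receive two additional requests by mail and are then telephoned to collect study data. At a minimum, vital status is ascertained". Section 1 repeats the minimum: "For non-respondents, vital status will be ascertained". Section 2 also foresees lost participants, in the setting of confirming deaths: "if participants are lost to follow-up), we search the National Death Index Plus".

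Three other provisions bear on how much HF could go unseen:
- The run-in "phase was designed to eliminate poor compliers prior to randomization".
- The Medicare linkage does not depend on a questionnaire: "Each year, we will obtain Medicare Data Files through ResDAC". The plan concedes that "CMS might be more likely to capture older subjects (65+ years), women, and white participants".
- The power section assumes five years of mean follow-up with little loss. It states no percentage.

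**The concern.** The primary outcome is HF hospitalization. A death-index search finds deaths, not non-fatal admissions. A living participant who no longer replies and is not visible in Medicare data therefore has unknown HF status, yet none of the three listed end points stops the clock. Taken literally, that unknown time is counted as event-free.

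The direction of the error is fixed: person-time is kept while events are missed, so absolute HF rates and the planned cumulative incidence curves read low in both primary aims. If loss also differed by arm, the hazard ratio could move. Two analysts could also build slightly different datasets from the same text.

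**Working it through.** The plan gives no figure for this point, so there is none to reproduce. The check asks how large the literal reading's error could be.

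**Inputs from the plan.** N = 25,871; five years; HF rate h = 8.29 per 1,000 person-years (Primary Aim 1, Statistical power); 63% aged 65 or over and age 67 ± 7 years (Table 1).

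**Assumptions.** HF hazard is constant and deaths are ignored. A fraction L stops replying for good, at times uniform over 0 to 5 years. A share c of these is still seen through Medicare. The plan gives neither L nor c.
- L = 1% to 2% is the reading of little loss; 5% to 10% is a stress case.
- c uses age as a proxy. The lower value is 63%, the baseline share aged 65 or over. The upper value takes ages as normal, 67 ± 7, with everyone aged 65 or over captured. The share aged 65 or over is then 61% at t = 0 and 84% at t = 5, and averages 77% when weighted by t, because unobserved time builds up late.
- c = 0 ignores the linkage and is an upper bound.

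**No loss.** Five-year incidence is 1 − exp(−0.00829 × 5) = 4.06%. Events are 25,871 × 0.0406 = 1,050. The relative standard error of the rate is 1/√1,050 = 3.1%.

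**Literal reading.** The unobserved share of person-time is about L(1 − c)/2. For L = 2% and c = 63% this is 0.02 × 0.37/2 = 0.37%. Integrating exactly over the loss times gives:

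| Loss L | Cover c | Rate per 1,000 | Relative shift | Events missed |
|---|---|---|---|---|
| 1% | 77% | 8.28 | −0.1% | 1.2 |
| 2% | 63% | 8.26 | −0.4% | 3.9 |
| 5% | 77% | 8.24 | −0.6% | 6.0 |
| 10% | 63% | 8.14 | −1.9% | 19.3 |
| 1% | 0 | 8.25 | −0.5% | 5.2 |
| 2% | 0 | 8.21 | −1.0% | 10.4 |
| 5% | 0 | 8.08 | −2.5% | 26.1 |
| 10% | 0 | 7.87 | −5.0% | 52.2 |

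At 1% to 2% loss with cover, the shift is 0.04 to 0.12 standard errors, and the 4.06% incidence reads 0.005 to 0.015 percentage points low. At 5% to 10% loss with cover, the shift is 0.2 to 0.6 standard errors. The relative shifts are the same at the plan's lower rate of 6.19.

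**Hazard ratio, equal loss.** Both arms lose the same share of events, so the ratio cancels. A true 0.82 reads 0.820 in every row.

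**Hazard ratio, unequal loss.** Take 5% in one arm, 6% in the other and no cover. A true ratio of 1 reads (1 − 0.025)/(1 − 0.030) = 1.005. The standard error of the log hazard ratio is about 2/√1,050 = 0.062, so a one-point imbalance moves the estimate by about 0.08 standard errors.

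**The case for a change.** The strongest case for a change is that the three-part list is the only definition of risk time in the plan. Variable follow-up can arise from HF, death or staggered entry alone, so the phrase about follow-up lengths supplies no last-contact date. The assumed Medicare cover may also be generous. The case definition in Section 2 needs record review, a signed release is described only for participants who report HF themselves, and the plan does not say how a Medicare-only case in a non-responder would be confirmed. If it could not be, the no-cover rows apply. An extra clause costs little.

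Most of this stands as a description of the text. The no-cover rows at 1% to 2% loss still show only 0.5% to 1.0%, and they leave the hazard ratio alone.

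Other features of the plan make the with-cover rows too high rather than too low. Questionnaires go out every year, so a later reply can report an earlier admission. Records sought from next of kin after a death may reveal one. HF risk probably rises with age, and so does Medicare cover. If risk doubled every ten years (an assumption), effective cover would be about 89% rather than 77%, and missed events at 1% to 2% loss would fall to about 0.6 to 1.1.

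Censoring at last known status is not clearly better either. It is informative if people stop replying because they are ill. If events are counted only within that time, confirmed admissions found later are discarded. And if Medicare enrolment is treated as known HF status, the uncertainty about Medicare-only cases remains.

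**Conclusion.** No change to the plan is needed. The list of end points is incomplete as written, but the gap is one that analysts fill by ordinary censoring, and the stated reason for using the Cox model points that way. If the list were followed to the letter, the absolute rate would read 0.1% to 0.4% low at 1% to 2% loss with 63% to 77% Medicare cover, or 0.5% to 1.0% low with no cover. The primary result, the hazard ratio, would stay at 0.820 for a true 0.82.

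This rests on two assumptions that the plan does not quantify: loss really is small, and it is about equal by arm. The run-in, the repeated contact attempts and the double-blind design support them. Loss of 5% to 10% with no linkage would take the rate 2.5% to 5.0% low, but that contradicts the plan's expectation of little loss and ignores its linkage. Even then, equal loss would leave the hazard ratio at 0.820.
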